10.4 Routine Adverse Event Reporting

All Adverse Events **must** be reported in routine study data submissions. **Adverse events reported expeditiously through CTEP-AERS must also be reported in routine study data submissions in Medidata Rave.**

Adverse event data collection and reporting, which are required as part of every clinical trial, are done to ensure the safety of patients enrolled in the studies as well as those who will enroll in future studies using similar agents. Adverse events are reported in a routine manner at scheduled times during the trial using Medidata Rave. For this trial the Adverse Event CRF is used for routine adverse event reporting in Rave.

10.5 Pregnancy

Although not an adverse event in and of itself, pregnancy as well as its outcome must be documented via **CTEP-AERS**. In addition, the **Pregnancy Information Form** included within the NCI Guidelines for Adverse Event Reporting Requirements must be completed and submitted to CTEP. Any pregnancy occurring in a patient or patient's partner from the time of consent to 90 days after the last dose of study drug must be reported and then followed for outcome. Newborn infants should be followed until 30 days old. Please see the "NCI Guidelines for Investigators: Adverse Event Reporting Requirements for DCTD (CTEP and CIP) and DCP INDs and IDEs" (at http://ctep.cancer.gov/protocolDevelopment/adverse_effects.htm) for more details on how to report pregnancy and its outcome to CTEP.

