3.1.16 Pregnancy Precaution: Men and women should avoid pregnancy for seven months after the date of their last treatment with Lutetium Lu 177 Dotataate. It is noteworthy that β -HCG may be secreted by a small percentage of NETs, such that, in addition to being a pregnancy marker, it also is a tumor marker. Consequently, NET female patients with positive β -HCG (>5 mIU/mL) at baseline can be eligible to enter the study and receive treatment if pregnancy can be excluded by lack of expected doubling of β -HCG and negative pelvic ultrasound. Normally, in pregnant subjects β -HCG doubles every 2 days during the first 4 weeks of pregnancy and every 3.5 days by Weeks 6 to 7. Women of childbearing potential include any female who has experienced menarche and who has not undergone successful surgical sterilization (hysterectomy, bilateral tubal ligation, or bilateral ovariectomy) or is not postmenopausal (defined as amenorrhea >12 consecutive months, and for women on hormone replacement therapy, only with a documented plasma follicle-stimulating hormone (FSH) level >35 mIU/mL). Even women who are using oral, implanted, or injected contraceptive hormones, an intrauterine device (IUD), or barrier methods (diaphragm, condoms, spermicidal) to prevent pregnancy, are practicing abstinence or where the partner is sterile (e.g., vasectomy) should be considered to be of childbearing potential. Postmenopausal women who have fertilized eggs implanted are also considered to be of childbearing potential. Acceptable methods of contraception may include total abstinence at the discretion of the Investigator in cases where the age, career, lifestyle, or sexual orientation of the patient ensures compliance. Periodic abstinence (e.g., calendar, ovulation, symptothermal, post-ovulation methods) and withdrawal are not acceptable methods of contraception. Reliable contraception (hormonal or barrier method of birth control; abstinence) should be maintained throughout the study and for 7 months after study treatment discontinuation. All women of childbearing potential and male partners must use a double-barrier method of birth control or practice continuous abstinence from heterosexual contact throughout the study and for seven months after the end of the last treatment.

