6.1.1 Triapine

Patients will be instructed to take triapine PO at the assigned dose level. Triapine will be administered on Days 1-14 of every 8 week cycle to overlap with the four administrations of Lutetium Lu 177 Dotataate. On Day 1 of each cycle, patients will ingest one dose of triapine within 90 minutes after Lutetium Lu 177 Dotataate treatment. Triapine will be discontinued after the last cycle of Lutetium Lu 177 Dotataate administration since triapine does not have anti-tumor activity by itself.

Patients will be asked to fast (except for water) for 2 hours prior to dosing and for 1 hour after ingesting the oral dose. Capsules should not be opened.

Missed doses for any reason, including vomiting, can be taken up to 6 hours after the scheduled dose. If it has been more than 6 hours since the missed dose, this dose should be skipped.

6.1.2 Lutetium Lu 177 Dotataate:

Lutetium Lu 177 dotataate and related supportive care drugs will be administered per participating institution standard operating procedure per FDA approved label indication, dose and route of administration. Please refer to section 8.2.1 for details regarding Lutetium Lu 177 Dotataate route of administration.

Somatostatin Analogs: If patients were on somatostatin analog long acting release (SSA-LAR) depot injections prior to enrollment in the trial, they will continue to be on SSA LAR during the trial. Patient will need to discontinue long-acting somatostatin analogs for at least 4 weeks prior to initiating Lutetium Lu 177 dotataate unless long-acting somatostatin analog is required for control of patients carcinoid syndrome. Patient can receive either long acting octreotide 30 mg every 4 weeks as deep intramuscular depot injection or lanreotide 120 mg every 4 weeks as deep subcutaneous injection, per FDA guidelines. Injections are administered in the superior external quadrant of the buttock.

Patients who need rescue short-acting octreotide to control their functional neuroendocrine symptoms per recommendations of their treating physician.

Antiemetic: Administer antiemetics 30 minutes before the recommended amino acid solution.

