6.5 Duration of Therapy

In the absence of treatment delays due to adverse event(s), treatment may continue for 4 cycles or until one of the following criteria applies:

- Disease progression (patient will however be monitored for OS)
- Intercurrent illness which would, in the judgment of the investigator, a) affect assessments of clinical status to a significant degree, b) require discontinuation of drug, or c) both a and b
- Unacceptable adverse event(s)
- Delay in treatment of more than 6 weeks.
- Patient decides to withdraw from the study
- General or specific changes in the patient's condition render the patient unacceptable for further treatment in the judgment of the investigator
- Clinical progression
- Patient non-compliance
- Pregnancy
 - All women of child-bearing potential should be instructed to contact the investigator immediately if they suspect they might be pregnant (e.g., missed or late menstrual period) at any time during study participation.
 - The investigator must immediately notify CTEP in the event of a confirmed pregnancy in a patient participating in the study.
- Termination of the study by sponsor

- The drug manufacturer can no longer provide the study agent

The reason(s) for protocol therapy discontinuation, the reason(s) for study removal, and the corresponding dates must be documented in the Case Report Form (CRF).

In April-May 2022 there was a global shortage of Lutetium 177 dotatate. Study enrollment and treatment was held per NCI CTEP's recommendation. The study was not affected as all patients had received cycle 1 of treatment had cleared DLT window. Delay in treatment due to global shortage will not trigger protocol deviation and treatment will resume when drug supply is restored. Patient will then get back on treatment schedule per protocol.

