6.6 Duration of Follow-Up

Patients will be followed for 24 months from the time of enrollment *or* until death, whichever occurs first. Patients removed from study for unacceptable adverse event(s) will be followed until resolution or stabilization of the adverse event.

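### Section 10.5 ends pregnancy reporting and outcome follow-up 90 days after the last dose, short of the seven-month avoidance period in 3.1.16; the firm gap is late partner pregnancies and late outcome follow-up

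*Combined protocol and SAP*

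**What the plan says.** Three sections of the combined protocol and SAP deal with pregnancy, and they use different clocks.

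- **Section 10.5 (Pregnancy).** A pregnancy in a patient or a patient's partner "from the time of consent to 90 days after the last dose of study drug must be reported" and followed for outcome. It is documented in CTEP-AERS with a Pregnancy Information Form, and newborns are followed to 30 days of age. For further detail the section points to NCI guidelines.
- **Section 3.1.16 (Pregnancy Precaution).** "Men and women should avoid pregnancy for seven months after the date of their last treatment" with Lutetium Lu 177 Dotatate. Reliable contraception "should be maintained throughout the study and for 7 months after study treatment discontinuation". A double-barrier method or abstinence applies "throughout the study and for seven months after the end of the last treatment". All three sentences give seven months, but each words the starting point differently.
- **Section 6.5 (Duration of Therapy).** Pregnancy is listed among the criteria for stopping treatment. Under it stands: "The investigator must immediately notify CTEP in the event of a confirmed pregnancy in a patient participating in the study". No time limit is given, and partners are not mentioned.

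Two further passages fix the timing. Section 6.1.1 states: "Triapine will be administered on Days 1-14 of every 8 week cycle", while lutetium is given on Day 1. Section 6.6 states: "Patients will be followed for 24 months from the time of enrollment", or until death if that comes first.

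**The concern.** A partner pregnancy beginning in, say, the fifth month after treatment falls inside the period in which 3.1.16 asks patients to avoid pregnancy. Section 10.5 nevertheless does not require it to be reported or its outcome recorded. For a patient's own pregnancy at the same time, 6.5 may require notice to CTEP, but nothing explicitly requires the form, the CTEP-AERS record or follow-up of the outcome.

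What is at stake is completeness of safety information. Section 3.2.11 describes both agents as potentially teratogenic or abortifacient, and section 2.5.1.2 says that no preclinical or clinical data exist for the combination. Any exposed pregnancy with a known outcome, including a normal one, would be informative.

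**Working it through.** There is no calculated figure in the plan to reproduce: 90 days and seven months are stated rules. The check compares the two windows.

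**Inputs.** Reporting window: 90 days after the last dose of study drug (10.5). Avoidance period: seven months after the last treatment (3.1.16). Cycle length: 56 days, four cycles, lutetium on Day 1 and triapine on Days 1-14 (6.1 and 6.1.1). Month length is an assumption: 30.44 days, so 7 × 30.44 = 213 days.

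**Post-treatment share outside 10.5.** Formula: (avoidance days − days covered) / avoidance days.

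- *Both clocks start on the same date:* 213 − 90 = 123 days; 123 / 213 = 57.8%.
- *Seven months from the last lutetium dose (Day 1), 90 days from the last triapine dose (Day 14, 13 days later):* days covered = 13 + 90 = 103; 213 − 103 = 110 days; 110 / 213 = 51.7%.

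**Sensitivity to month length.**

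| Seven months taken as | Same start | Lutetium start / triapine start |
|---|---|---|
| 196 days (28-day months) | 106 days, 54.1% | 93 days, 47.4% |
| 210 days | 120 days, 57.1% | 107 days, 51.0% |
| 212 days (shortest calendar span) | 122 days, 57.5% | 109 days, 51.4% |
| 213 days | 123 days, 57.8% | 110 days, 51.7% |
| 215 days (longest calendar span) | 125 days, 58.1% | 112 days, 52.1% |

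Only 28-day months combined with different start dates bring the share below half.

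**Share if treatment time is counted.** Section 10.5 covers the whole treatment period. From Cycle 1 Day 1 to Cycle 4 Day 1 is 3 × 56 = 168 days; to the last triapine dose it is 168 + 13 = 181 days.

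- *Seven months from last lutetium:* 110 / (168 + 213) = 110 / 381 = 28.9%.
- *Seven months from last triapine:* 123 / (181 + 213) = 123 / 394 = 31.2%.

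This assumes four cycles without delay. A patient who stops early has a higher share. Counting the time from consent to first dose would lower it slightly.

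**Does existing follow-up reach the end of the seven months?** Assume treatment starts 30 days after enrollment (the limit in 4.4), four cycles are given, and the seven months run from the last triapine dose.

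- *No delay:* 30 + 168 + 13 + 213 = day 424.
- *Three delays of 6 weeks (the limit in 6.5):* 424 + 3 × 42 = day 550.
- *Follow-up under 6.6:* 24 months, about day 730.

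Both fall inside follow-up. Only an extreme case, three delays of 16 weeks (the discontinuation threshold in 7.1), would pass it: 424 + 3 × 112 = day 760.

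**What each section requires after day 90, up to seven months.**

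| | Patient pregnancy | Partner pregnancy |
|---|---|---|
| 10.5: CTEP-AERS, form, outcome | not required | not required |
| 6.5: notice to CTEP | required on its wording; not if read as on-treatment only | not mentioned |

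**The case against.** The strongest objection is section 6.5. Its wording covers any confirmed pregnancy in a participating patient and sets no 90-day limit. It also asks women of childbearing potential to report a suspected pregnancy at any time while on study. Since the seven months normally end well inside the 24-month follow-up, a reader who infers from 10.5 alone that every pregnancy after day 90 escapes reporting goes too far. That part of the objection stands, and it limits the point to partners and to outcome follow-up. It does not remove the point: 6.5 does not mention partners, the form or outcomes, and its place under duration of therapy lets a site read it as on-treatment only.

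A reader might also infer that more than half of the whole exposure window is missed. That holds for the post-treatment part only; with treatment time included, the share is about 30%. Nor does the protocol call the seven months a risk period, or say that a reporting window must equal a contraception period. Some difference could be a deliberate choice, although no reason is given.

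Section 10.3.3 gives partial cover. It classes a congenital anomaly as serious and requires late serious events attributed to treatment to be reported. At most this captures some adverse outcomes; it does not record the pregnancies themselves or the normal outcomes. The NCI guidelines to which 10.5 refers are not part of the documents, so whether they set a longer window cannot be checked here.

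Finally, the practical yield is small. The trial has 29 patients, pregnancies will be few, and accrual has closed (2.5.2.1). Some time still remained when this version was issued on 17 May 2023. Sections 2.5.2.1 and 5.5.3.4 together place closure no later than 13 December 2022. A patient enrolled on that date and treated without delay would reach day 424 in February 2024; earlier closure shortens this.

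**Conclusion.** The concern holds in limited form. Sections 10.5 and 3.1.16 use different periods without explanation, and 110 to 123 of about 213 post-treatment days (52-58% on a 30.44-day month) lie outside the 10.5 window. The firm gap has two parts: partner pregnancies after day 90, and CTEP-AERS documentation with outcome follow-up for patient pregnancies after day 90. If 6.5 is read as on-treatment only, notice of late patient pregnancies is missing as well.

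The documents do not support the broader conclusion that late pregnancies go wholly unreported. Nor do they show any effect on the primary analysis: DLT is assessed at the end of Cycle 1, and no DLT, RP2D, sample-size or efficacy figure depends on this rule. This is a modest, inexpensive improvement to safety data collection. It takes no position on how long pregnancy should be avoided.

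**What to change.** Reconcile sections 3.1.16, 6.5 and 10.5:

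- In 10.5, make the reporting and outcome follow-up window, for patients and partners, run at least as long as the avoidance period that the protocol itself sets in 3.1.16. On the present text this takes the window from 90 to about 213 days, about 123 days more, and leaves none of the post-treatment avoidance period outside it.
- Use one start date in all the sentences concerned. At present 3.1.16 refers to the last lutetium treatment, to treatment discontinuation and to the end of the last treatment, while 10.5 refers to the last dose of study drug.
- Cross-refer 6.5 and 10.5, and state in 6.5 whether the duty to notify continues after treatment ends.

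The cost is a few lines of text and possibly a few extra reports. Patients are already seen every three months up to 24 months from enrollment, so no visits need to be added except in the extreme delay case above. Partners are not study participants, so information about their pregnancies has to be obtained through the patient.

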10.6 Secondary Malignancy

A *secondary malignancy* is a cancer caused by treatment for a previous malignancy (e.g., treatment with investigational agent/intervention, radiation or chemotherapy). A secondary malignancy is not considered a metastasis of the initial neoplasm.

CTEP requires all secondary malignancies that occur following treatment with an agent under an NCI IND/IDE be reported expeditiously via CTEP-AERS. Three options are available to describe the event:

- Leukemia secondary to oncology chemotherapy (e.g., acute myelocytic leukemia [AML])
- Myelodysplastic syndrome (MDS)
- Treatment-related secondary malignancy

Any malignancy possibly related to cancer treatment (including AML/MDS) should also be reported via the routine reporting mechanisms outlined in each protocol.

10.7 Second Malignancy

A second malignancy is one unrelated to the treatment of a prior malignancy (and is **NOT** a metastasis from the initial malignancy). Second malignancies require **ONLY** routine adverse event reporting unless otherwise specified

11. STUDY CALENDAR

Baseline evaluations are to be conducted within 30 days prior to start of protocol therapy. Scans and x-rays must be done ≤ 4 weeks prior to the start of therapy. In the event that the patient's condition is deteriorating, laboratory evaluations should be repeated within 48 hours prior to initiation of the next cycle of therapy.

	Screening	Pre-treatment ^a	Cycle 1 (8 weeks)							Cycle 2 (8 weeks)							Cycle 3 (8 weeks)							Disease Progression	Follow-Up and Off-Treatment Visits ^{b,c}			
			Day 1 ^c	Day 9	Day 14 ^c	Day 15 ^c	Day 29 ^c	Day 43 ^c	Days 44-56	Day 1 ^c	Day 14 ^c	Day 29 ^c	Days 30-56	Day 1 ^c	Day 14 ^c	Day 29 ^c	Days 30-56	Day 1 ^c	Day 14 ^c	Day 29 ^c	Days 30-56	Day 1 ^c	Day 14 ^c	Day 29 ^c	Days 30-56			
Triapine			A-----A							A-----A				A-----A			A-----A											
Lutetium Lu 177 Dotataate			B							B				B			B											
Informed consent	X																											
Demographics	X																											
Medical history	X																											
Concurrent meds	X		X-----X																									
Physical exam	X		X				X			X		X		X		X		X		X		X				X		
Vital signs	X		X				X			X		X		X		X		X		X		X				X		
Height	X																											
Weight	X		X				X			X		X		X		X		X		X		X				X		
Performance status ^d	X		X				X			X		X		X		X		X		X		X				X		
CBC w/diff, plts	X		X				X	X	X		X		X		X		X		X		X		X			X		
Comprehensive Chemistry Panel ^e	X		X				X	X	X		X		X		X		X		X		X		X			X		
EKG (as indicated)	X																											

NCI Protocol #: 10388
 Version Date: 17.May.2023

	Screening	Pre-treatment ^a	Cycle 1 (8 weeks)								Cycle 2 (8 weeks)								Cycle 3 (8 weeks)								Disease Progression	Follow-Up and Off-Treatment Visits ^{b,c}
			Day 1 ^c	Day 9	Day 14 ^c	Day 15 ^c	Day 29 ^c	Day 43 ^c	Days 44-56	Day 1 ^c	Day 14 ^c	Day 29 ^c	Days 30-56	Day 1 ^c	Day 14 ^c	Day 29 ^c	Days 30-56	Day 1 ^c	Day 14 ^c	Day 29 ^c	Days 30-56	Day 1 ^c	Day 14 ^c	Day 29 ^c	Days 30-56			
Ga-DOTATATE PET/CT Scan ^f (or 64-Cu DOTATATE PET/CT scan)	X																											
Adverse event evaluation			X-----X																								X	
Radiologic evaluation (CT/MRI Scan) ^g	X ^h		Radiologic measurements should be performed every 8 weeks in the dose escalation cohort. Radiologic measurements should be performed every 12 weeks in the dose expansion cohort.																								X	
Pregnancy test ⁱ	X																											
24-Hour Urine 5HIAA ^j			X																				X ^j		X ^j			
blood collection (EDTA) for 1.3.3 – frozen blood will be biobanked for future analysis in lieu of hPG80 assay			X																								X	
ctDNA blood collection (Streck)			X																								X ^k	
Deoxyribonucleosides blood collection (EDTA) ^l			X								X																X	
Tumor tissue collection ^m		X																										
PK blood collection ⁿ				X																								

NCI Protocol #: 10388
 Version Date: 17.May.2023

	Screening	Pre-treatment ^a	Cycle 1 (8 weeks)							Cycle 2 (8 weeks)					Cycle 3 (8 weeks)					Cycle 4 (8 weeks)					Disease Progression	Follow-Up and Off-Treatment Visits ^{b,c}
			Day 1 ^c	Day 9	Day 14 ^c	Day 15 ^c	Day 29 ^c	Day 43 ^c	Days 44-56	Day 1 ^c	Day 14 ^c	Day 29 ^c	Days 30-56	Day 1 ^c	Day 14 ^c	Day 29 ^c	Days 30-56	Day 1 ^c	Day 14 ^c	Day 29 ^c	Days 30-56					
Methemoglobin Level by peripheral venous blood ^o			X	X																						

STUDY CALENDAR NOTES:

A: Triapine: Dose as assigned on Days 1-14 of each cycle. Cycle length = 8 weeks
The recommended Phase 2 Dose of Triapine was determined to be: 150mg once a day on Days 1-14 of each cycle. Cycle length = 8 weeks

B: Lutetium Lu 177 Dotatate: 200 mCi IV, Day 1 of each cycle for a total of 4 doses. Cycle length = 8 weeks.

a: Pre-treatment collections should be preferably collected on a separate day from screening, but may be collected on the same day at the discretion of the site.

b: Follow-up checks and surveillance CT/MRI scans to be conducted every 3-months for 24 months from the time of enrollment *or* until death, whichever occurs first. Patients removed from study for unacceptable adverse event(s) will be followed until resolution or stabilization of the adverse event. Additional scan not needed at the end-of-study visit.

c: Cycles 1-4 visit windows: Days 9,14 +/- 2 days. All other visits +/- 3 days.
Visit windows for Follow-up (Q3-mos visits): \pm 3 weeks visit windows.
The following exception applies to visit windows: Dosing of Lu-177 dotatate cannot be given prior to scheduled date. It can be delayed per visit windows in appropriate situations.

d: Performance status evaluations should be evaluated every 4 weeks.

e: Albumin, alkaline phosphatase, total bilirubin, bicarbonate, BUN, calcium, chloride, creatinine, glucose, LDH, phosphorus, potassium, total protein, SGOT [AST], SGPT [ALT], sodium.

f: To be performed if NETSPOT, DETECTNET (64Cu dotatate scan) or Octreoscan has not been performed within 6 months.

g: 7 days +/- window is allowed for scans to accommodate logistical issues in obtaining timely scans for unforeseeable circumstances.

h: To confirm progression within the last 3 years.

i: Pregnancy test for women of childbearing potential.

j: 24-Hour Urine 5HIAA should be collected prior to dosing Lutetium Lu-177 dotatate. 24 Hr Urine 5HIAA should be collected unless in exceptional circumstances that patient cannot collect or deliver a 24-Hr sample, alternative 5HIAA assessment per institutional standard can be allowed.
5HIAA will also be collected at the end of PRRT treatment (clinic visit for Cycle 4 Day 29) or at disease progression, whichever happens first. If patient does not receive all 4 doses of PRRT then 24 Hr Urine 5HIAA can be collected at the end-of-treatment visit for that particular patient.

k: Optional collection.

l: Two 8mL K2 EDTA white top tubes will be collected at three timepoints for all participants on C1D1 (pre-treatment), on C2D1 (pre-treatment), and at disease progression.

m: If archival tissue within the last 6 months is not available, a fresh biopsy will be mandatory.

Screening	Pre-treatment ^a	Cycle 1 (8 weeks)							Cycle 2 (8 weeks)							Cycle 3 (8 weeks)							Cycle 4 (8 weeks)							Disease Progression	Follow-Up and Off-Treatment Visits ^{b,c}
		Day 1 ^c	Day 9	Day 14 ^c	Day 15 ^c	Day 29 ^c	Day 43 ^c	Days 44-56	Day 1 ^c	Day 14 ^c	Day 29 ^c	Days 30-56	Day 1 ^c	Day 14 ^c	Day 29 ^c	Days 30-56	Day 1 ^c	Day 14 ^c	Day 29 ^c	Days 30-56	Day 1 ^c	Day 14 ^c	Day 29 ^c	Days 30-56							

n: PKs: To be collected in the dose-escalation cohort only.

PK time points on Cycle 1, Day 9 (+/- 1 day) include: Pre, 0.5, 1, 1.5, 2, 3, 4, 6, 8 hours.

PK WINDOWS:

Pre dose: within 30 minutes

30 minutes: +/- 5 minutes

60 minutes: +/- 5 minutes

1 hour 30 minutes: +/- 5 minutes

2 hours: +/- 5 minutes

3 hours: +/- 10 minutes

4 hours: +/- 10 minutes

6 hours: +/- 10 minutes

8 hours: +/- 10 minutes

o: Methemoglobin: to be collected in dose-escalation cohort only, on Cycle 1 Day 1 and Cycle 1 Day 9.

Methemoglobin timepoint on Cycle 1 Day 1 is pre-treatment.

Methemoglobin timepoints on Cycle 1 Day 9 (+/- 1 day) include: Pre, 0.5, 1, 1.5, 2, 3, 4, 6, 8 hours, i.e., blood is to be drawn at each of the PK blood draws.

Methemoglobin Windows for C1D9 are:

Pre dose: within 30 minutes

30 minutes: +/- 5 minutes

60 minutes: +/- 5 minutes

1 hour 30 minutes: +/- 5 minutes

2 hours: +/- 5 minutes

3 hours: +/- 10 minutes

4 hours: +/- 10 minutes

6 hours: +/- 10 minutes

8 hours: +/- 10 minutes

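### Pregnancy testing is scheduled only at Screening, with no repeat before Lu-177 doses 2 to 4; under this version few doses, possibly none, remain to be affected

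*Combined protocol and SAP*

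**What the plan says.** The pregnancy-test row of the Section 11 calendar has one mark, in the Screening column, where one-off items such as consent and height also have theirs. Note i names the population, "Pregnancy test for women of childbearing potential", and stops there. The calendar's opening text says: "Baseline evaluations are to be conducted within 30 days prior to start of protocol therapy". Note B sets Lu-177 at "200 mCi IV, Day 1 of each cycle for a total of 4 doses", with an 8-week cycle, and note A adds triapine on Days 1–14 of each cycle. Note c gives the visit window ("All other visits +/- 3 days") but does not let Lu-177 be given early.

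Section 3.2.11 excludes pregnant women because of the possible effect of both agents on a fetus, and 6.5 lists pregnancy among the reasons to end treatment. Section 3.1.16 requires double-barrier contraception or continuous abstinence during the study and for seven months afterwards. Its rule for a positive beta-HCG is written for baseline. Section 6.5 adds that "All women of child-bearing potential should be instructed to contact the investigator immediately if they suspect they might be pregnant".

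**The concern.** The protocol treats pregnancy as a bar to treatment at entry and throughout therapy, but schedules a check of that condition only once, before the first dose. Three further 200 mCi administrations follow, each with two weeks of a ribonucleotide reductase inhibitor. If contraception fails and the woman has not noticed, a site that follows the calendar exactly meets no scheduled check before the next dose. What is at stake is fetal exposure to both agents. No estimate, endpoint or error rate depends on it.

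**Working it through.** **Step 1. Does any other item schedule a test?**

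- The chemistry panel (note e) lists "Albumin, alkaline phosphatase, total bilirubin, bicarbonate, BUN, calcium, chloride, creatinine, glucose, LDH, phosphorus, potassium, total protein", then the transaminases and sodium. Beta-HCG is not in it.
- The laboratory repeat before a cycle is conditional. It applies when the patient's "condition is deteriorating, laboratory evaluations should be repeated within 48 hours prior to initiation of the next cycle of therapy". It does not name a pregnancy test, and a pregnant woman need not be deteriorating.
- Section 10.5 says that "pregnancy as well as its outcome must be documented via" the adverse-event system. That is reporting of a known pregnancy, not detection.
- Sections 6.1.2 and 8.2 leave Lu-177 administration to site procedure and the FDA label, and 8.2 points to the package insert. Neither section mentions pregnancy testing.

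None of these schedules a test after Screening.

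**Step 2. How old is the only scheduled result at each dose?**

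Inputs: 56-day cycles (notes A and B); test taken s days before dose 1, with s = 0 to 30 (baseline window, taken to cover Screening).

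Age at dose k = (k − 1) × 56 + s.

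| Dose | Days since dose 1 | Age of result, s = 0 to 30 |
|---|---|---|
| 2 | 56 | 56–86 days |
| 3 | 112 | 112–142 days |
| 4 | 168 | 168–198 days |

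Permitted slippage only lengthens this. Adding 3 days at each of three cycles gives 198 + 9 = 207 days at dose 4. A full 6-week delay before each of doses 2–4 gives 3 × (56 + 42) + 30 = 324 days.

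**Step 3. Which doses could still be given under this version (17 May 2023)?**

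Section 2.5.2.1 says the unsuitability of frozen blood was recognised after accrual had closed. Section 5.5.3.4 dates the switch to biobanking to 13 December 2022. So accrual had closed by that date at the latest. Section 4.4 asks for treatment to start within 30 days of registration.

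For the latest possible registrant with the full 30-day lag, dose 1 falls on 13 Dec 2022 + 30 d = 12 Jan 2023. Then:

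- dose 2: 12 Jan + 56 d = 9 Mar 2023 (with one 42-day delay, 20 Apr 2023);
- dose 3: 12 Jan + 112 d = 4 May 2023, so it falls after 17 May only if delayed by more than 13 days;
- dose 4: 12 Jan + 168 d = 29 June 2023 (30 May 2023 with a same-day start).

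Working back for an undelayed dose 4 after 17 May 2023:

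- 30-day start lag: 17 May 2023 − 198 d = registration after 31 Oct 2022;
- same-day start: 17 May 2023 − 168 d = registration after 30 Nov 2022;
- one delay at the 6-week limit of 6.5, with the 30-day lag: 31 Oct − 42 d = registration after 19 Sept 2022.

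The documents do not give the last registration date, so they do not show that anyone falls in these windows.

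**Step 4. How many women?**

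Section 9.2 plans 15 female patients among 29. Women of childbearing potential are not counted separately, so 15 is only a ceiling for the whole trial.

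**The case against.** The strongest reply has three parts.

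First, the protocol delegates Lu-177 administration to site procedure and the label. If those require a test before every dose, what is missing is a line of text and not a protection. This stands as a limit: neither source can be seen here. It does not answer the point, because the reviewed text does not say that a test is required.

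Second, safeguards continue on treatment: mandatory contraception, immediate self-report, discontinuation for pregnancy, and physical examinations at cycle visits. These are substantial, and how often to test is partly a design judgement. But contraception can fail and self-report needs suspicion. Section 3.1.16 itself still classes women who use contraception, are abstinent or have a sterile partner as being of childbearing potential. Nausea, vomiting and fatigue are listed as likely with triapine (10.1.1), so early symptoms could plausibly be put down to treatment; that is an inference, not a documented event.

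Third, accrual is over. Undelayed doses 2 and 3 are past for every patient under the dates above, and dose 4 may be too. This stands fully, and it limits what an amendment could now achieve.

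A reader might infer that women were dosed without a current test. The documents do not support that: they show what was scheduled, not what sites did. Nor do they support multiplying three doses by 15 women as exposure still to come.

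**Conclusion.** The gap in the schedule is real. One test is scheduled, at Screening, and the text provides no repeat before doses 2, 3 and 4, when the result is 56–86, 112–142 and 168–198 days old. The lower ends follow directly from the cycle length; the upper ends rest on reading Screening as part of the 30-day baseline window, which is reasonable but not stated.

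For this version the practical reach is small. It is confined to an undelayed dose 4 in a patient registered after 31 October 2022, or to a delayed dose. The number may be zero, and the time needed to approve an amendment would reduce it further. These dates assume closure by 13 December 2022, inferred from two sections, and a start within 30 days of registration.

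Severity is minor. It is a patient-safety point and changes no endpoint.

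**What to change.** Extend the pregnancy-test row and note i: for women of childbearing potential, one urine or serum test shortly before each remaining Lu-177 dose, at the latest on Day 1 before the infusion. If it is positive, hold both agents until pregnancy is excluded by the work-up in 3.1.16 (beta-HCG trend and pelvic ultrasound), which should be extended from baseline to on-treatment results. A woman with a known HCG-secreting tumor could test positive every time; for her, use a quantitative serum beta-HCG compared with her baseline value. If site procedure or the label already requires a pre-dose test, one sentence in note i saying so is enough.

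The cost is one inexpensive test per remaining dose. Had it applied from the start, it would have been 3 tests per woman over doses 2–4, at most 15 × 3 = 45, not counting work-up of positives. Day 1 is already a visit.

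The downside is a positive first seen on Day 1. Section 3.1.16 gives a doubling time of 2 to 3.5 days, or 48 to 84 hours. At 84 hours the work-up outlasts both the 72-hour shelf life in 8.2 and the 3-day visit window, so the vial may be lost and the dose delayed, though a delay of that length is within the 6-week limit of 6.5. Testing some days earlier would lower that risk. The documents give no ordering, cancellation or laboratory turnaround times from which to set an exact day, so that choice is best left to the site.
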